## 10.4 CONTINUING CONSENT

Subjects for whom consent was initially obtained from a LAR, but who subsequently regain decision-making capacity while in hospital, will be approached for consent for continuing participation, including continuance of data acquisition. The consent form signed by the LAR should reflect that such consent will be obtained.

## 10.5 WITHDRAWAL OF CONSENT

Patients may withdraw or be withdrawn (by the LAR) from the trial at any time without prejudice. Data recorded up to the point of withdrawal will be included in the trial analysis, unless consent to use their data has also been withdrawn. If a patient or LAR requests termination of the trial drug during the treatment period, the drug will be stopped but the patient will continue to be

followed up as part of the trial. If a patient or LAR withdraws consent during trial treatment, the trial drug will be stopped but permission will be sought to access medical records for data related to the trial. If a patient or LAR wishes to withdraw from the trial after completion of trial treatment, permission to access medical records for trial data will be sought.

## 10.6 IDENTIFICATION OF LEGALLY AUTHORIZED REPRESENTATIVES

Many of the patients approached for participation in this research protocol will invariably have limitations of decision-making abilities due to their critical illness. Hence, most patients will not be able to provide informed consent. Accordingly, informed consent will be sought from the potential subject's legally authorized representative (LAR).

Regarding proxy consent, the existing federal research regulations ('the Common Rule') states at 45 CFR 46.116 that "no investigator may involve a human being as a subject in research...unless the investigator has obtained the legally effective informed consent of the subject or the subject's legally authorized representative"; and defines at 45 CFR 46 102 (c) a legally authorized representative (LAR) as "an individual or judicial or other body authorized under applicable law to consent on behalf of a prospective subject to the subject's participation in the procedures(s) involved in the research." The Office of Human Research Protections (OHRP) defined examples of "applicable law" as being state statutes, regulations, case law, or formal opinion of a State Attorney General that addresses the issue of surrogate consent to medical procedures. Such "applicable law" could then be considered as empowering the LAR to provide consent for subject participation in the research. Interpretation of "applicable law" may be state specific and will be addressed by the PETAL central IRB.

According to a previous President's Bioethics Committee (National Bioethics Advisory Committee (NBAC)), an investigator should accept a relative or friend of the potential subject who is recognized as an LAR for purposes of clinical decision making under the law of the state where the research takes place [68]. Finally, OHRP has stated in their determination letters that a surrogate could serve as a LAR for research decision making if such an individual is authorized under applicable state law to provide consent for the "procedures" involved in the research study [69].

## 10.7 JUSTIFICATION OF SURROGATE CONSENT

According to the Belmont Report, respect for persons incorporates at least two ethical convictions; first, that individuals should be treated as autonomous agents, and second, that person with diminished autonomy are entitled to protection. One method that serves to protect subjects is restrictions on the participation of subjects in research that presents greater than minimal risks. Commentators and research ethics commissions have held the view that it is permissible to include incapable subjects in greater than minimal risk research as long as there is the potential for beneficial effects and that the research presents a balance of risks and expected direct benefits *similar* to that available in the clinical setting [70]. Several U.S. task

forces have deemed it is permissible to include incapable subjects in research. For example, the American College of Physicians' document allows surrogates to consent to research involving incapable subjects only "if the net additional risks of participation are not substantially greater than the risks of standard treatment." [71]. Finally, NBAC stated that an IRB may approve a protocol that presents greater than minimal risk but offers the prospect of direct medical benefits to the subject, provided that "the potential subject's LAR gives permission..." [68]

Consistent with the above ethical sensibilities regarding the participation of decisionally incapable subjects in research and the previous assessment of risks and benefits in the previous section, the present trial presents a balance of risks and potential direct benefits that is **similar** to that available in the clinical setting, with the exception of the additional blood draws.

## 10.8 ADDITIONAL SAFEGUARDS FOR VULNERABLE SUBJECTS

The present research will involve subjects who might be vulnerable to coercion or undue influence. As required in 45CFR46.111 (b), we recommend that sites utilize additional safeguards to protect the rights and welfare of these subjects. Such safeguards might include, but are not limited to: a) assessment of the potential subject's capacity to provide informed consent, b) the availability of the LAR to monitor the subject's subsequent participation and withdrawal from the study; c) augmented consent processes. The specific nature of the additional safeguards will be left to the discretion of the central IRB, in conjunction with the sites.

## 10.9 CONFIDENTIALITY

Federal regulations at 45 CFR 46 111 (a) (7) requires that when appropriate, there are adequate provisions to protect the privacy of subjects and to maintain the confidentiality of data. To maintain confidentiality, all laboratory specimens, evaluation forms, and reports will be identified only by a coded number. The coded number will be generated by a computer, and only the study team will have access to the codes. All records will be kept in a locked, password protected computer. All computer entry and networking programs will be done with coded numbers only. All paper case report forms will be maintained inside a locked office. Study information will not be released without the written permission of the patient, except as necessary for monitoring by the National Heart, Lung, and Blood Institute, and the PETAL Clinical Coordinating Center.

# 11 ADVERSE EVENTS

## 11.1 SAFETY MONITORING

Assuring patient safety is an essential component of this protocol. Each participating investigator has primary responsibility for the safety of the individual participants under his or her care. The Investigators will determine daily if any adverse events occur during the period from enrollment through **study day 7** (five days after infusion of study drug) or ICU discharge, whichever occurs first.

The following adverse events will be collected in the adverse event case report forms:

- Serious adverse events
- Nonserious adverse events that are considered by the investigator to be related to study drug or study procedures or of uncertain relationship (Appendix C2)
- Adverse events that lead to permanent discontinuation of the study drug infusion
- Hypersensitivity reactions to cisatracurium, severe prolonged bradycardia (heart rate < 50 for > 30 minutes), and paralysis recall
- Hypotension or pneumothorax, considered by the investigator to be related to high PEEP, or of uncertain relationship.

A clinical trial adverse event is any untoward medical event associated with the use of a drug or study procedure in humans, whether or not it is considered related to a drug or study procedure.

After randomization, adverse events related to protocol procedures or occurring after the patient receives the first dose of study drug must be evaluated by the investigator. If the adverse event is judged to be reportable, as outlined above, then the investigator will report to the CCC their assessment of the potential relatedness of each adverse event to protocol procedure or study drug via electronic data entry. Investigators will assess if there is a reasonable possibility that the study drug or procedure caused the event, based on the criteria outlined in Appendix C2. Investigators will also consider if the event is unanticipated or unexplained given the patient's clinical course, previous medical conditions, and concomitant medications.

If a patient's treatment is discontinued as a result of an adverse event, study site personnel must report the circumstances and data leading to discontinuation of treatment in the adverse event case report forms.

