## 11.2 SERIOUS ADVERSE EVENTS

Serious adverse event collection begins after the patient or surrogate has signed informed consent and has received study drug or undergone study procedures. If a patient experiences a serious adverse event after consent, but prior to receiving study drug, the event will NOT be collected unless the investigator feels the event may have been caused by a protocol procedure.

Study site personnel must alert the CCC of any **serious and study drug or study procedure related** adverse event within 24 hours of investigator awareness of the event. Alerts issued via telephone are to be immediately followed with official notification on the adverse event case report form. See Appendix C for reporting timelines for serious, unexpected, study related events (SAEs) and serious, unexpected suspected adverse reactions (SUSARs)

As per the FDA and NIH definitions, a serious adverse event is any adverse event that results in one of the following outcomes:

- Deaths

- A life-threatening experience (that is, immediate risk of dying)
- Prolonged inpatient hospitalization or rehospitalization

As per <http://www.fda.gov/Safety/MedWatch/HowToReport/ucm053087.htm>: Report if admission to the hospital or prolongation of hospitalization was a result of the adverse event. Emergency room visits that do not result in admission to the hospital should be evaluated for one of the other serious outcomes (e.g., life-threatening; required intervention to prevent permanent impairment or damage; other serious medically important event).

- Persistent or significant disability/incapacity

As per <http://www.fda.gov/Safety/MedWatch/HowToReport/ucm053087.htm>: Report if the adverse event resulted in a substantial disruption of a person's ability to conduct normal life functions, i.e., the adverse event resulted in a significant, persistent or permanent change, impairment, damage or disruption in the patient's body function/structure, physical activities and/or quality of life.

Important medical events that may not result in death, be life-threatening, or require hospitalization may be considered serious adverse events when, based upon appropriate medical judgment, they may jeopardize the patient and may require medical or surgical intervention to prevent one of the outcomes listed in this definition.

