Serious adverse events will be collected during the first **7 study days** or until ICU discharge, whichever occurs first, regardless of the investigator's opinion of causation. Thereafter, serious adverse events are not required to be reported unless the investigator feels the events were related to either study drug or a protocol procedure.

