## **C3. CLINICAL OUTCOMES THAT MAY BE EXEMPT FROM ADVERSE EVENT REPORTING**

[figure not shown]
Study-specific clinical outcomes of ARDS, as outlined in Sections 3.8.1 and 3.8.2 (Primary and Secondary Outcomes) and Section 6.3 (Assessments During the Study) are exempt from adverse event reporting unless the investigator deems the event to be related to the administration of study drug or the conduct of study procedures (or of uncertain relationship). The following are examples of events that will be considered study specific clinical outcomes

- Death not related to the study drug or procedures.
- Cardiovascular events: need for vasoactive drugs or fluids for hypotension or hypotension.
- Respiratory events: decreased PaO2/FiO2, hypoxia, worsening acute respiratory distress syndrome, or respiratory failure.
- Hepatic events: hepatic injury or liver dysfunction that leads to an increase from baseline in the serum level of bilirubin.
- Renal events: renal failure, renal insufficiency, or renal injury that leads to an increase from baseline in serum creatinine.
- Hematologic/coagulation events: coagulopathy, disseminated intravascular coagulation, thrombocytopenia, or thrombocytosis.

Note: Arrhythmias such as heart block, ventricular tachycardia or ventricular fibrillation are not considered study specific clinical outcomes and should be recorded as adverse events if they are serious events, are considered by the investigator to be related to study drug, or lead to discontinuation of the study drug infusion.

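### Several adverse event collection rules turn on study drug, which only the cisatracurium arm receives, so the unblinded arms are not counted alike; size and net direction are unknown

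*Protocol*

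**What the plan says.** Protocol 1.2 defines study drug as the randomly assigned cisatracurium, and 5.1.1 explains why it is not blinded.

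- **Collection (11.1).** Investigators check daily for adverse events from enrollment to study day 7 or ICU discharge, whatever the arm. The list of what goes on the form then includes "Nonserious adverse events that are considered by the investigator to be related to study drug or study procedures or of uncertain relationship (Appendix C2") and "Adverse events that lead to permanent discontinuation of the study drug infusion". Severe prolonged bradycardia and paralysis recall are listed with no relatedness test. Hypotension and pneumothorax are listed if attributed to high PEEP or uncertain.
- **Evaluation (11.1).** Once a patient is randomized, "adverse events related to protocol procedures or occurring after the patient receives the first dose of study drug must be evaluated by the investigator".
- **Exempt outcomes (Appendix C3).** Hypotension, hypoxia, organ dysfunction and similar outcomes are all "exempt from adverse event reporting unless the investigator deems the event to be related to the administration of study drug or the conduct of" trial procedures; an uncertain relationship also brings them back in. A Note says heart block and ventricular arrhythmias are not exempt: they are recorded if serious, or if they "are considered by the investigator to be related to study drug, or lead to discontinuation of the study drug infusion".
- **Serious events (11.2).** "Serious adverse event collection begins after the patient or surrogate has signed informed consent and has received study drug or undergone study procedures". Then: "If a patient experiences a serious adverse event after consent, but prior to receiving study drug, the event will NOT be collected unless" a protocol procedure is, in the investigator's view, a possible cause. The section ends by requiring collection for 7 study days or until ICU discharge, "regardless of the investigator's opinion of causation".
- **Use of the counts.** SAP 2.5 compares events by weighted Poisson regression (nonserious 1, serious 2), by organ class and preferred term. Under Appendix C, a DSMB finding that the overall rate is higher on cisatracurium leads to notice to the central IRB and the FDA within 15 days.

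**The concern.** A between-arm comparison of event counts is fair only if an event of the same kind has the same chance of being recorded in each arm. Here one entry route, attribution to study drug, exists in one arm only, and the person making the attribution knows the arm. A background event in a cisatracurium patient can be put down to the drug and recorded. The same event in a control enters only if it is put down to a procedure or called uncertain. Even open-label cisatracurium given to a control under 5.2.1 is not study drug by the definition in 1.2.

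The start of serious event collection is also tied to a drug that controls never receive. At stake is how the DSMB and readers interpret a difference in nonserious events, or in a preferred term made up partly of them. The plan has no analysis limited to events collected by the same rule.

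**Working it through.** **Step 1. The rules by arm.**

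| Rule | Cisatracurium | Control |
|---|---|---|
| Nonserious, drug-attributed (11.1) | open | closed |
| Nonserious, procedure-attributed or uncertain (11.1) | open | open |
| Event that permanently stops the infusion (11.1) | open | cannot occur |
| Required evaluation (11.1) | all events after first dose, plus procedure-related | procedure-related only |
| Exempt outcome re-entered (C3) | drug, procedure, uncertain | procedure, uncertain |
| Heart block, ventricular arrhythmia (C3 Note) | serious, drug-attributed, infusion-stopping | serious only |
| Serious event once collection has begun (11.2) | any cause | any cause |

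The Note omits the procedure-related and uncertain routes that 11.1 allows, so the two places disagree.

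**Step 2. The serious event clock.** Three readings of the second sentence of 11.2:

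- *Literal.* Controls never receive study drug, so nearly all their serious events would be barred. This contradicts the preceding sentence, which starts collection at drug or procedures, and the closing rule on causation.
- *Workable.* Active patients lose the time to first dose, 0 to 4 hours (4.4). Controls start at their first procedure; specimens are due within 2 hours (6.3.3). The share lost is L = (active hours − control hours)/168. With 4 and 0 hours, 4/168 = 2.4%; with 4 and 2 hours, 2/168 = 1.2%; with equal times, 0. These assume events spread evenly over 7 days. If all fell in the first 72 hours, the ceiling would be 4/72 = 5.6%.
- *Before study treatment starts, in either arm.* No meaningful asymmetry.

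**Step 3. Illustrations only.** The plan gives no adverse event rate to reproduce. The one figure borrowed is the maximum of 1408 patients, taken as 704 per arm (1:1 allocation assumed). A fixed-sample calculation for 35% v 27%, two-sided 0.05 and power 0.90 gives 701 per arm, 1402 in total, so 1408 is not in dispute. Counts are independent Poisson with no true harm. Per patient, s nonserious events are collected alike, S are serious, and x are background events misattributed to the drug on cisatracurium only. All three are assumed.

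*Nonserious events.* With a = 704(s + x) and c = 704s, the ratio is a/c, and the chance of a nominal excess is Φ(ln(a/c)/√(1/a + 1/c) − 1.96). For s = 0.1 and x = 0.01: a = 77.44, c = 70.4, ratio 1.10, chance 8.4%, against 2.5% when x = 0. Over s = 0.05 to 0.3 and x = 0.005 to 0.02, the ratio runs from 1.02 to 1.40 and the chance from 4% to 33%.

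*One arrhythmia term, SAP weights.* Take 1% serious in both arms (2.4% of these lost on active) and 0.2, 0.5 or 1.0 percentage points nonserious on cisatracurium only, as the Note alone would have it. A nominal excess then occurs in 3.4%, 6.2% or 13.9% of trials, against 2.1% with none. If controls contribute half as many through the 11.1 routes, 13.9% falls to about 6%.

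*All events, SAP weights.* The ratio is [s + x + 2S(1 − L)]/(s + 2S), and the two effects cancel at x = 2SL. With L = 4/168, that is x = 0.005, 0.010 or 0.019 for S = 0.1, 0.2 or 0.4. For S = 0.2 and s = 0.1, x = 0.005, 0.01 or 0.02 gives 0.991, 1.001 or 1.021. With L = 2/168 and x = 0.005, the ratio is (0.1 + 0.005 + 0.3952)/0.5 = 1.0005 instead of 0.991. The sign depends on inputs the documents do not supply.

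**The case against.** Much of the rule is common to both arms. The daily check in 11.1 is arm-neutral. Serious events are collected for 7 days whatever their cause. Controls also undergo study procedures (high PEEP, low tidal volume, start-up steps), so the procedure-related and uncertain routes are real for them, and hypotension has its own PEEP bullet. Events that the drug truly causes should appear mainly on the drug; only misattributed background events are artefact. Relatedness is recorded for each reported event, so much of the breakdown could be tabulated from planned data. Deaths, organ failure, rescue procedures, pneumothorax, supraventricular arrhythmia and paralysis recall are compared as outcomes regardless of attribution. The Appendix C trigger is a DSMB judgement that leads to notification.

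All of this stands, and it limits the harm. It does not open the drug route to controls, reconcile the Note with 11.1, or repair the second sentence of 11.2.

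A reader might infer that the plan will produce a false cisatracurium excess and a spurious FDA notice. The documents do not support that: no misattribution rate is given, and the clock can offset the effect in the all-event total. Nor do they support the inference that control serious events go uncollected, because that reading contradicts the sentences on either side of it.

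**Conclusion.** The defect is real but minor. Several collection and evaluation rules depend on a drug given to one arm of an unblinded trial, and the counts feed a between-arm comparison. Part of a cisatracurium excess in nonserious events, or in exempt outcomes re-entered by attribution, may reflect misattribution of background events under the rule. How much cannot be computed from the documents, and every percentage for a nominal excess rests on assumed rates.

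The clock's direction depends on how 11.2 is read. On the workable reading the active arm loses about 0 to 2.4% of a 7-day window, if events are evenly spread. It is therefore not established that the clock offsets the attribution effect, and the net direction for all events is open. Mortality, organ failure, the other outcomes collected regardless of attribution, efficacy and the stopping boundaries are unaffected.

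**What to change.** 1. **Protocol 11.1, 11.2 and Appendix C3.** Collect and evaluate events in both arms from randomization through study day 7 or ICU discharge. Collect serious events regardless of causation, except the C3 exempt outcomes. Delete the sentence in 11.2 that cuts off events before study drug. Add the procedure-related and uncertain-relationship routes to the arrhythmia Note, so that it matches 11.1.
2. **SAP 2.5 and the DSMB report.** Keep the all-event analysis and the Appendix C notification trigger as they are. Add one comparison restricted to events collected alike in both arms: serious events without the C3 exempt outcomes, severe prolonged bradycardia, and paralysis recall. Tabulate drug-attributed and infusion-stopping events separately beside it. Give procedure-attributed, PEEP-attributed and uncertain events their own row, as open to both arms but subject to unblinded judgement.

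The cost is edited wording, a few more serious event forms for the hours before the first dose, and one extra analysis. No patients or measurements are added, and no cisatracurium signal is removed from testing or notification.

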- a) Oxygenation Index on study days 1-4,7
- b) PaO2 / FiO2 ratio on study days 1-4, 7
- c) Level of PEEP on study days 1-4, 7
- d) Plateau pressure on study day 1-4, 7
- e) Development of pneumothorax through day 7

9. Long term outcome assessments

We will assess seven measures after hospitalization:

- a) Disability: using Katz Activities of Daily Living (ADL)/Lawton Instrumental Activities of Daily Living Scale (IADL) plus two additional Nagi items
- b) Health-Related Quality of Life (including utilities): EuroQol (EQ-5D-5L)
- c) Self-rated health: 1 standard item
- d) Pain-interference: 1 standard item
- e) Post-traumatic Stress-like Symptoms: Post-Traumatic Stress Symptoms (PTSS-14)
- f) Cognitive function: Montreal Cognitive Assessment (MoCA-Blind) or, via proxy, the Alzheimer's Disease 8 (AD8)
- g) Subsequent return to work, hospital and ED use, and location of residence

These measures will be collected through telephone interviews with patients or their LARs (Appendix G).

10. Use of rescue procedures

Rescue procedures will be chosen according to the practice at the clinical site. We will record the use of the following rescue procedures (yes/no) through study day 28: prone positioning, nitric oxide, epoprostenol sodium, high frequency ventilation, and ECMO.

11. Paralysis recall, in-hospital

Paralysis recall assessment will be monitored once during hospitalization in all patients, using a modified Brice questionnaire [22, 23].

12. Supraventricular tachycardia (SVT) or new onset atrial fibrillation (the occurrence of one or more episodes during the ICU stay will be recorded)

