#### Other Reference Measurements

1. Manual muscle strength testing (MMT) screen and assessment on day 7, 14, 21 28 or until hospital discharge.
2. Assessment of gross motor movement on study day 3.
3. Paralysis recall assessment, in both study arms, one time during study hospitalization, using a modified Brice questionnaire [22, 23].

To facilitate the ability of the patient to interact appropriately with the above measures, sedative agents will be titrated according to the institution's sedation protocol. The MMT and the Modified Brice questionnaire will be conducted in patients who meet the awakening and comprehension criteria. Awakening and comprehension will be determined based upon the response of the patient to five commands ("open/close your eyes," "look at me," "open your mouth and stick out your tongue," "nod your head," and "raise your eyebrows when I have counted to five"). If the patient can respond appropriately to all five of these orders, the patient will be considered awake and able to comprehend and the above measures will be attempted to be obtained.

Additionally, prior to conducting the MMT the patient will be assessed for injuries or medical devices that would preclude the MMT assessment and for any safety barriers to strength training such as unstable shock, profound hypoxemia, unstable spine or airway, nonresponsive to verbal command (RASS -4 or -5). The Manual Muscle strength testing uses the MRC (Medical Research Council) score evaluates muscle strength with very good interobserver agreement, and was used in the ACURASYS trial [2, 32]. Introduced in 1970, the Brice questionnaire is a reliable and efficient method of detecting recall after sedation or general

anesthesia. This questionnaire avoids falsely identifying pre-sedation memories and experiences [22, 23].

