#### Paralysis recall, in-hospital

Paralysis recall assessment will be monitored once during hospitalization in all patients, using a modified Brice questionnaire. Paralysis recall will be counted if a patient answered "Yes" to "Do you remember anything between going to sleep and waking up?" and "unable to move or breathe". Paralysis recall can be indicated in both AE and Brice forms. We gather information from both places and treat missing as "NO" if a patient has an open BRICE form.

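### The paralysis-recall endpoint merges the Brice questionnaire with undefined adverse-event reports, so a patient without a questionnaire can be counted positive but never negative

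*Protocol*

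**What the plan says.** Protocol 3.9.2, item 11, names one instrument: "Paralysis recall assessment will be monitored once during hospitalization in all patients, using a modified Brice questionnaire". Protocol 6.3.2 (Other Reference Measurements) repeats that it is done once, in both arms, and limits it to patients who can be interviewed: "The MMT and the Modified Brice questionnaire will be conducted in patients who meet the awakening and comprehension criteria". The screen is a set of five commands.

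Protocol 11.1 opens a second route. Among the events for the adverse-event form it lists "Hypersensitivity reactions to cisatracurium, severe prolonged bradycardia (heart rate < 50 for > 30 minutes), and paralysis recall". Bradycardia gets a threshold there; recall gets neither a definition nor an instrument. Surveillance is daily and ends at study day 7 or ICU discharge, whichever is earlier.

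SAP Appendix A3 joins the two routes. It first gives a two-answer rule for the questionnaire ("Paralysis recall will be counted if a patient answered" yes both to remembering something and to having been unable to move or breathe). It then adds "Paralysis recall can be indicated in both AE and Brice forms" and "We gather information from both places and treat missing as" NO, on the condition "if a patient has an open BRICE form". SAP Appendix A1 classes the outcome as safety, binary, with Fisher's exact test. SAP 2.3 sets a two-sided 0.05 level with no multiplicity correction.

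**The concern.** The protocol's outcome is a proportion of patients interviewed in the same way. The SAP's outcome is a union of two sources that differ in reporter, definition and time window, and its rule for negatives rests on only one of them. Entry to the denominator can therefore depend on the outcome, and an undefined report can replace an answer from the defined questionnaire.

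The trial is open-label. Protocol 5.1.1 accepts that because the primary outcome, mortality, is objective. That argument does not extend to whether an investigator records recall as an adverse event. Protocol 3.6 (item 6) also faults the previous trial for leaving paralysis recall undetermined, so this outcome is meant to fill a stated gap. At stake are the reported recall proportion and its between-arm test.

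**Working it through.** **1. What the rule does to each kind of patient, read literally**

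| Brice form | Adverse-event report of recall | Classified as |
|---|---|---|
| Open, meets two-answer rule | Yes or no | Positive |
| Open, does not meet rule | No | Negative |
| Open, does not meet rule | Yes | Positive: the report overrules the interview, with no precedence rule given |
| None | Yes | Positive |
| None | No | Missing, because NO requires an open form |

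The last two rows are the denominator fault. The condition appears deliberate: the barotrauma rule in the same appendix also merges two forms, but treats missing as NO without any condition.

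**2. Inputs for the size**

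The documents give no recall rate, no number interviewed and no power for this outcome, so there is no figure of the plan's to reproduce. These are assumptions:

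- 400 patients per arm with a Brice result, and true recall p equal in both arms (1.5%, then 3%).
- Adverse-event-only positives K, Poisson with the means shown below, in patients without a Brice form. Each adds one to the numerator and one to the denominator.
- Fisher's exact test, two-sided 0.05 (from the SAP).

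With X ~ Binomial(400, p) in each arm (A active, C control), the table tested has positives X_A + K_A and X_C + K_C, and negatives 400 − X_A and 400 − X_C. The false-positive rate is the probability that Fisher's p is at most 0.05. Values are rounded; simulation and exact enumeration agree to within about half a percentage point.

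| Mean adverse-event-only reports, active : control | p = 1.5% | p = 3% |
|---|---|---|
| 0 : 0 | 2.5% | 3% |
| 2 : 0 | 5% | 5% |
| 4 : 0 | 12% | 9% |
| 3 : 1 | 5% | 5% |
| 2 : 2 | 3% | 4% |

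The base rate is below 5% because Fisher's test is conservative for rare events. The estimate still moves when the error rate does not. At p = 1.5% the expected Brice count is 400 × 0.015 = 6 per arm, so a 3:1 split gives (6 + 3)/403 = 2.2% against (6 + 1)/401 = 1.7%.

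**3. Wider range, with fixed counts**

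With 200 to 400 assessed per arm and recall of 1% to 2%, exact enumeration gives 0.5–2.8% with no extra reports, 2.4–4.1% for 2:0, 2.4–4.8% for 4:1 and 8.7–12.3% for 4:0.

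**4. One data set**

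Take 300 assessed per arm and 3 Brice positives in each (1.0% against 1.0%). Extra reports in the active arm only give:

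- 4 extra: 7/304 = 2.3%, p = 0.34
- 8 extra: 11/308 = 3.6%, p = 0.055
- 10 extra: 13/310 = 4.2%, p = 0.020

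If the 4 reports instead overrule Brice negatives, the active arm is 7/300 = 2.3%. The two routes are almost the same size.

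**The case against.** **The direction is not established.** A reader might infer that the test is biased toward more recall with cisatracurium. Investigators know the assignment, almost every active patient is paralyzed, and Protocol 11.1 says that "adverse events related to protocol procedures or occurring after the patient receives the first dose of study drug must be evaluated by the investigator". Since Protocol 1.2 defines study drug as the randomly assigned cisatracurium, the first-dose part of that sentence cannot apply to controls. But the same sentence also covers procedure-related events, which occur in either arm. The listed item and the daily surveillance start at enrollment for everyone, the time limit is the same in both arms, and Protocol 5.2.1 allows controls open-label cisatracurium. Reports falling mainly in the active arm is plausible, not documented. This objection stands.

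**The affected group may be tiny.** A patient who can describe recall by day 7 would usually pass the five-command screen and be interviewed. Recall found at an interview within the surveillance window may also be entered as an adverse event, so many reports will only duplicate Brice positives. This stands as to size.

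**The SAP may intend only patients with a Brice form to enter.** The wording can be read that way. The denominator fault then goes, but an undefined report can still overrule a Brice negative.

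**Two sources suit a rare harm.** An adverse-event-only report may be true recall that a single interview missed, and equal true recall is a test null rather than an expectation. This is fair, and it is a reason to keep such reports visible. It does not justify adding them to a test with no matching way of recording negatives.

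**Conclusion.** The point holds in a limited form. The SAP's derivation departs from the protocol's single-instrument definition, lets an undefined report overrule it, and, read literally, admits patients without a Brice form only when they are positive. The between-arm comparison can be biased, and the reported figure need not be a proportion of patients assessed.

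The stronger reading, that the comparison is biased against cisatracurium, is not supported: no counts are given and adverse-event surveillance covers both arms. The numerical effect is conditional. Under the assumptions of 400 assessed per arm and 1.5% recall in each, clear inflation of the error rate (to about 12%) needs an average of about four adverse-event-only reports, all in one arm. An average of two leaves it near 5%, and four split 3:1 or 2:2 keep it at or below 5%. This is a worthwhile correction of a safety outcome and does not affect the primary analysis.

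**What to change.** In SAP Appendix A3:

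1. Define the tested outcome from the Brice questionnaire by the existing two-answer rule, with patients who have a completed form as the denominator in both arms. The present wording refers to an open form and does not say whether open means completed.
2. State the number assessed per arm beside the result.
3. Report adverse-event-form recall separately by arm, including patients with no Brice form.
4. Show the combined count (Brice or adverse event) by arm as a sensitivity analysis, so that no harm signal is hidden.

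The cost is SAP wording; no new data are needed. There are two downsides. Recall reported only as an adverse event is outside the main Fisher comparison, which item 4 offsets. The Brice interview itself remains unblinded, which this change does not cure.
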